10.2.5.2 Beck Depression Inventory II

This 21-item scale (Beck et al., 1961) assesses common features of depression on a 4-point severity scale, with a focus on cognitions. It is widely used in both drug and psychosocial treatment studies of depression, and is commonly used in studies of pain (Dworkin et al., 2005). The BDI has also been

found in two studies (Rounsaville et al., 1979; Weiss et al., 1989) to be reliable in substance dependent patients. The BDI will be collected at baseline and monthly during Phase 1 and Phase 2.

10.2.5.3 Pain and Opioid Analgesics Use History

Information will be collected at the Phase 1 baseline visit to determine a variety of **pain-associated issues** (body region(s) affected by pain, participant description of pain diagnosis, duration of pain, number of days in past 30 days and past 6 months with pain, past history of pain if not currently experiencing pain; pain treatment history) and **opioid analgesics use issues** [initial reason for initiating opiate use (e.g. pain relief versus illicit use), current and past sources of opiate analgesics, current and past types of opioid analgesics].

10.2.5.4 CIDI Section E and Section K

Questions from Section E (Major Depressive Disorders) and Section K (PTSD) of the Composite International Diagnostic Interview (CIDI) (<http://www.crufad.unsw.edu.au/cidi/cidi.htm>; CIDI) will be administered during baseline by a trained and certified study staff member.

The results will be used to characterize the prescription opioid dependent population consistent with the exploratory research question of whether these disorders moderate the effect of treatment on outcome.

10.2.5.5 SF-36

The SF-36 version 2 is a 36-item, participant administered instrument examining health-related quality of life changes as a function of treatment (Ware and Sherbourne, 1992). Most items are rated on a 5-point scale. The SF-36 v. 2 will be completed at Phase 1 and Phase 2 baseline, and at the end of Phase 1 and Phase 2.

10.2.5.6 Fagerstrom Test for Nicotine Dependence

The Fagerstrom Test for Nicotine Dependence is a widely used assessment procedure for determining the level of nicotine dependence. The Fagerstrom will be completed at baseline and final follow-up visit.

10.2.5.7 Locator Information

Basic locator data will be collected and kept confidential in the participant's record. Locator information typically includes contact information such as residential street address, or an address of someone who knows where to contact the participant if they are homeless, and a phone number where they can be reached. Additional information includes the names and addresses of two or three individuals who would likely know their whereabouts, particularly relatives or close friends. This information will be obtained at baseline and will be updated as necessary. This information will be used to facilitate contact with the participant during the study and at follow-up.

10.2.6 Treatment Compliance

Medication compliance will be measured using pill counts done at the weekly SMM visits. Treatment participation will be measured using an SMM and EMM session CRF.

Participation in medical and psychosocial treatment and self-help outside of the study will be captured on a concomitant treatment CRF.

10.2.7 Process Measures

The DSMB Plan and protocol will not define a minimally effective dose for psychosocial treatments, as this amount is not known. However, the study executive group will monitor session attendance to identify study sites and clinicians with particularly low attendance rates, and implement a corrective action plan, as discussed in the Data and Safety Monitoring Plan.

10.2.7.1 Projected Timetable for Assessments

Please refer to Table 4.1 on page 4-5 and Table 4.2 on page 4-6 for Phase 1 and Phase 2 visit schedules.

10.3 Common Assessment Battery (CAB)

10.3.1 Brief Demographics Form

Basic demographic information assessing for age, ethnicity/race, and gender will be collected at baseline.

10.3.2 Addiction Severity Index (ASI) - Lite

The ASI Lite is a standardized, multidimensional, semi-structured, comprehensive clinical interview that provides clinical information necessary to formulate treatment plans as well as problem severity profiles in 6 domains commonly affected in substance abusers (McLellan et al., 1985). The domains include chemical abuse (alcohol and drug), medical, psychiatric, legal, family/social and employment/support. Composite Scores for each problem domain are derived mathematically and used as change measures or outcome indicators as a function of treatment intervention. The ASI Lite also provides clinically useful information on whether the participant is at imminent risk for suicidality, thus permitting evaluators to implement any needed immediate and/or early intervention strategies. A revised version of the ASI 5th Edition, 1997 version (ASI Lite) that includes only those questions used to derive the composite scores along with some demographic information will be administered by a research staff member having at least a bachelor's degree in the social sciences or equivalent training and experience as determined by the site's investigator. Composite scores will be calculated according to the methods described by McGahan et al., (1982), and Carroll et al., (1994). The ASI Lite will be administered at Phase 1 baseline. The ASI Lite Follow-up Assessment will be administered in Phase 1 at Week 12, and in Phase 2 at baseline as well as Week 24.

10.3.3 Risk Behavior Survey

This is a brief, 12-item (with multiple sub-items) interviewer-administered assessment of HIV risk behaviors including intravenous drug use and sexual risks. This survey will be utilized to assess degree of HIV-infection risk by looking at risk behavior. Measures will include extent and methods of past drug use, sexual preference, sexual history, and extent of unprotected sex; and assessment of travel to international locations of increased-HIV infection rates. This measure takes approximately 15 minutes to administer and will be collected at baseline.

10.3.4 Composite International Diagnostic Interview (CIDI)

The CIDI is a comprehensive, standardized instrument for assessment of mental disorders according to the definitions and criteria of ICD-10 and DSM-IV. It has been developed by the World Health Organization in consultation with numerous experts, and tested in many countries. As part of the CAB assessments, CIDI Section J (Alcohol Use Disorders) and Section L (Substance-related Disorders) will be used to assess addiction for baseline characterization and exclusion criteria purposes. Training on the proper use of the CIDI and its material will be provided to the CTP interviewer staff.

[figure not shown]

11.1 Overview of Study Design

The study will have two phases (see Figure 11.1 below). **Phase 1** is an initial treatment study for subjects meeting DSM-IV criteria for opioid analgesic dependence who do not require ongoing opioid treatment for pain. Initial treatment consists of BUP/NX for one month plus a random assignment to SMM or EMM. Participants are followed for two more months and treatment failure is assessed continuously. Phase 1 treatment failures are eligible for treatment in Phase 2. **Phase 2** is a stabilization treatment study for failures to initial treatment. Stabilization treatment consists of BUP/NX for three months plus a random assignment to SMM or EMM. The three months of treatment are followed by one month of taper and two months of follow up.

Figure 11.1 CTN-0030 Detailed Study Schema

11.2 General Analytic Strategy

11.2.1 Significance Testing

All hypotheses will be tested by two-sided tests with level of significance $\alpha=0.05$. All exploratory analyses will be reported as such and will be thoroughly described in any publication. In particular, the modeling strategy for identification of predictors of outcome (such as inclusion of multiple covariates and interactions) will be explained in detail to allow adequate assessment of the strength of inferences based on data-driven statistical models.

11.2.2 Preliminary Analysis

Prior to the analysis of the primary hypothesis, the distributions of the outcome measures will be examined and possible outliers identified. Outliers will be thoroughly checked for collection or entry errors and will not be used in the analysis unless confirmed as correct and valid data. The final decision to include in the analysis outliers remaining (after data cleaning) will be based on discussion with the Lead Investigator (who will be blind to treatment assignment) and will depend on the individual outlying values.

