7.4.2.2 Procedures for Discontinuation

If EMM, SMM, or BUP/NX treatment is discontinued, either participant-initiated or investigator-initiated, the participant may continue to participate in the other study treatments; except if SMM is discontinued, he/she can not continue to receive BUP/NX. In most cases when all components of the participant's study treatment is discontinued, only study research visits will be expected from that point forward. Occasionally, a participant who has discontinued from study treatment may elect to return to one or more components of treatment. In this case, if the participant remains appropriate and within the treatment window based on the randomization date, the participant may be allowed to return to treatment. This may occur in Phase 1 or Phase 2 (up to the final day of the week 8 SMM visit window in Phase 2). As such, if a participant discontinues BUP/NX in Phase 2 and wishes to be restarted on BUP/NX, re-induction of BUP/NX can occur in Phase 2 until week 8 only.

Upon completion of the tapering phase, or in cases of early dropout, participants may continue in treatment at the CTP (if available), or may be referred to available local treatment resources. In the event that any participant desires additional pharmacological treatment for his/her opiate dependence, or if the study staff finds that additional treatment is clinically indicated, the site will refer the participant to a local provider of methadone or buprenorphine.

Participants whose clinical status worsens substantially during the study (e.g., increased opioids use, needle use, more dangerous behaviors such as overdose) may be referred to other treatment options; for instance, participants will be told about methadone maintenance as well as more intensive psychosocial treatment, or participants who relapse to regular opioids use in the context of severe and/or worsening pain may be referred to a pain clinic if clinically appropriate. All such participants will remain part of the study and will continue to be followed for research. A decision as to whether it is appropriate for such participants to continue with study treatment will be made by the local study medical clinician in consultation with the Lead Investigator (LI) or designee.

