7.6 Binding

This is an open-label study.

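### Section 11.2.2 lets outliers that have survived data cleaning be left out case by case once their values are seen, which can bias the continuous secondary and exploratory comparisons

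*Protocol*

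**What the plan says.** Protocol section 11.2.2 handles outliers in two steps, before the primary hypothesis is analysed.

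- Step 1: outliers are checked for errors of collection or entry, and they "will not be used in the analysis unless confirmed as correct and valid data".
- Step 2: "The final decision to include in the analysis outliers remaining (after data cleaning) will be based on discussion with the Lead Investigator", a person "who will be blind to treatment assignment". The decision "will depend on the individual outlying values".

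Three other places bear on this. Section 11.2.3 places the primary analyses on everyone randomized in each phase. Section 7.6 states: "This is an open-label study". Section 7.4.2.2 deals with participants whose clinical status worsens substantially; whether they stay on study treatment "will be made by the local study medical clinician in consultation with the Lead Investigator (LI) or designee".

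**The concern.** Step 1 is close to ordinary data cleaning. The difficulty is step 2. After errors have been looked for, it allows a value to be left out on a judgement made with that value in view. Whether an observation enters the analysis then depends on the outcome itself.

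The continuous measures are craving on the VAS, BPI, BDI and SF-36. These are bounded instruments, so an extreme score within range is a possible true score. In a trial of relapse, a surge in craving or depression is part of what the treatment may change. If extremes are more frequent in one arm, or are judged differently by arm, removing them shifts the estimated difference. The one stated protection is that the Lead Investigator is blind, so it matters whether the protocol supports that statement.

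**Working it through.** **1. What is left for step 2.** Values found to be errors are dealt with in cleaning. Read literally, values that cannot be confirmed are already held out by step 1. What remains consists of values that passed the check. On a looser reading, step 2 also covers values that could be neither confirmed nor refuted. On both readings they are not known errors, and the stated basis for the decision is the value itself.

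**2. Which analyses it reaches.**
- Primary outcomes: success or failure in Phase 1 and substantial improvement in Phase 2 are yes/no. Section 11.2.4 assigns a status to every patient, and sections 11.3.3.3 and 11.4.3.3 count those who discontinue as failures or as not improved. A yes/no status has no outliers.
- Numbered hypotheses: 1.1, 2.1 and 2.3 use these statuses, and 2.2 uses positive or negative urines. All are binary.
- Continuous measures: VAS, BPI, BDI and SF-36 are listed as secondary in sections 11.3.2.2 and 11.4.2.2. Treatment effects on craving, pain and quality of life are placed among the exploratory analyses (11.3.4.1 for all three; 11.4.5 for pain and craving). This is where step 2 can act.

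**3. Against the protocol's own condition.** Section 11.2.4 says that inference from incomplete data is valid if missingness does not depend on the unobserved value. A score set aside because it is extreme is missing because of its value. Step 2 can therefore create the kind of missingness that this condition rules out.

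**4. The blind.** Section 7.4.1 counts EMM and SMM among the study treatments, so a consultation under 7.4.2.2 about continuing treatment could reveal the arm. Section 12.2.1.6 also brings deaths and unexpected or study-related SAEs to the Lead Investigator. The protocol does not say how assignment is kept from that person. Equally, it does not say that assignment is disclosed, and a designee may be the one consulted.

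**5. Size.** The outlier rule carries no figure of its own.

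A check on the primary analysis, from Table 11.1: success 20% v 30%, n = 648, two-sided 0.05, taking 1:1 allocation (324 per arm).
- Power = Φ{[0.10·√324 − 1.96·√(2·0.25·0.75)] / √(0.20·0.80 + 0.30·0.70)} = Φ{(1.800 − 1.200)/0.608} = Φ(0.986) = 83.8%.
- The protocol states 84%. The figure reproduces, and nothing in this point changes it.

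An illustration for one continuous outcome with Phase 2 numbers (324 in total, 162 per arm). The exclusion rates and the distance of 3 SD are assumptions with no basis in the documents.
- SE of the mean difference = √(2/162) = 0.111 SD.
- 3% v 1% excluded: shift ≈ (0.03 − 0.01)·3 = 0.06 SD = 0.54 SE. A 5% test with no true difference rejects about 8.4% of the time.
- 5% v 1% excluded: shift ≈ (0.05 − 0.01)·3 = 0.12 SD = 1.08 SE. It rejects about 19% of the time.
- Equal exclusion, same direction: shift = 0.

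A simulation (lognormal outcome with log-SD 1, 162 per arm, no true effect, outlier defined as above the pooled mean plus 3 SD, about 6.5 such values per trial, Welch t-test, 20,000 runs) gave these type I errors:
- all values kept: 4.9%
- outliers dropped regardless of arm: 4.8%
- outliers dropped from one arm only: 14.5%

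Inflation of the test size needs removal that differs by arm. The simulation does not cover a true effect. If EMM does reduce extreme scores, removal that ignores arm would still delete part of that effect.

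**The case against.** The strongest case on the other side has five parts.

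- Holding out values that cannot be confirmed is routine cleaning. This stands, and it is why the point is directed at step 2.
- A reader might infer that section 11.2.2 removes real outcomes from the primary ITT analysis. The documents do not support that. Section 11.2.3 defines ITT by participants, and the primary statuses are binary and assigned to all of them. Dropping one weekly score does not drop a participant, because the GEE models accept incomplete series. One indirect route stays open: an outlying self-report count that feeds a binary status. The text does not address it.
- A reader might also infer that the blind must fail because treatment is open-label. That does not follow. Open-label delivery does not prevent the Lead Investigator from reviewing values without arm labels. Section 7.4.2.2 concerns only participants who worsen substantially, and it allows a designee. What stands is a tension that the protocol leaves unresolved.
- The assumed exclusion rates are arbitrary, and 3 SD may be rare or out of reach on a bounded scale. Craving in section 11.4.5 is modelled over 12 weeks, so if 3% of participants each lost one weekly score, only 3%/12 = 0.25% of the scores would go. This stands, and the figures serve as illustration only.
- Outlier definitions and sensitivity tables commonly belong in a SAP. This is right, and their absence is not the complaint. The complaint is the rule that section 11.2.2 does state.

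**Conclusion.** The point holds in a limited form. Section 11.2.2 allows values that are not known errors to be excluded at discretion after they are seen, so exclusion can depend on the outcome. The exposure is confined to the continuous secondary and exploratory comparisons; the primary outcomes, the numbered hypotheses and the sample size are essentially unaffected.

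The documents give no outlier frequency, so the size of the bias cannot be stated. If removal ignores arm and there is no treatment effect, the type I error stays near 5%. It rises only if removal differs by arm, and whether that happens turns largely on a blind that is neither secured in the text nor shown to fail. The point is minor, but the remedy costs almost nothing.

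**What to change.** Rewrite section 11.2.2 as follows.

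- Exclude a value only if it is confirmed as an error, meaning out of range for the instrument or contradicted by source.
- Keep every other value in the main analysis, including values that can be neither confirmed nor refuted.
- Show results without flagged outliers only as a sensitivity analysis.
- Have any remaining flag decided on arm-masked listings by someone with no role in participant-level decisions. Keep the commitment to blind review and state how it is secured, consistently with sections 7.4.2.2 and 7.6.

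The cost is a change of wording and one sensitivity table. Sample size, power and the primary analysis stay as they are.

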11.2.3 Intent to Treat (ITT) and Completer Samples

The primary analyses will be on the ITT samples; i.e., on all participants randomized in Phase 1 and all randomized subjects in Phase 2.

11.2.4 Missing Data and Dropouts

Every possible effort will be made to assess all patients in both Phase 1 and Phase 2. Despite our thorough and proactive approach to taking complete measurements on all randomized study patients at all time points, it is expected that there will be cases when assessments will be incomplete or missing.

Accounting for dropout in the analysis. The primary qualitative outcome measures, success/failure in Phase 1 and substantial improvement (yes/no) in Phase 2 will be determined for all study patients, regardless of whether they completed the treatment in these phases or not (see *Treatment Success/Failure for Dropout and Missing Data* on page 11-7 and *Substantial Improvement Status for Dropout and Missing data* on page 11-10). The analysis of the quantitative outcomes, measuring severity of symptoms and positive/negative weekly urines will be based on generalized linear models and Generalized Estimating Equations (GEE) models [Diggle, PJ, Liang K-Y, and Zeger, SL (1994) *Analysis of Longitudinal Data*, Oxford University Press, Oxford]. The GEE methodology requires no parametric distribution assumption, provides robust inference with respect to misspecification of the covariance, and allows analysis of continuous, categorical, and count data which may be missing for some patients either because of a missed week or due to drop-out. Thus, complete information for all patients is not needed. PROC GENMOD in SAS (2003) will be used to carry out these analyses.

The inferences from incomplete or missing data are valid provided that the missing data are missing at random (Little and Rubin, 1987). “Missing at random” means that the missing mechanism does not depend on the value of the unobserved outcome. Unfortunately, this assumption is untestable in most medical research, as in this study.

Sensitivity analyses will be used to address the impact of missingness on conclusions. One approach to this problem is to assume a model for the missingness mechanism that does depend on the unobserved outcome value and to do the analysis (i.e., estimate the treatment effect) incorporating the assumed model for the missingness. There are parametric and semi-parametric methods for doing so (Diggle and Kenward, 1994; Kenward 1998; Rotnitzky et al., 1998; Scharfstein et al., 1999; Lu et al., 1999). Comparison of the inferences from assuming various models for the missingness provide a measure of the validity of the efficacy estimate from the model that assumes missing “at random.” Another approach to sensitivity analysis is based on computation of a local sensitivity index, which measures the change in the estimated treatment effect in a neighborhood of the “missing at random” model for missingness (Ma and Heitman, 2005; Liu and Liang, 1997).

In the analysis of the secondary outcome measure status (positive/negative) of weekly urines over time, when urines are missing but a piece of “hard” data is available that the participant has used drugs, a positive urine status will be imputed. Examples of “hard” data indicating use include self-report of use or knowing that the participant entered an opiate treatment program or an inpatient detoxification program.

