The *Manual for EMM of Opioid Dependence* by Pantalon, Fiellin, Schottenfeld, Gordon, and O'Connor, was chosen because it meets all of the criteria listed above. This manual was used in a similarly designed study (Fiellin et al., 2002), in which opioid dependent participants were randomly assigned to either SMM or EMM, both delivered in a primary care setting. The EMM was delivered by primary care nurses who did not have drug-counseling experience. Thus, the manual is somewhat simpler than what might be delivered in a drug abuse treatment program. While such simplification is not ideal, the alternative, a standard drug counseling manual such as that by Mercer and Woody (1992), would present the opposite problem; it would be too complicated for delivery in a primary care setting. Therefore, the Pantalon et al. manual was chosen because of the greater likelihood of widespread adoption of this treatment if it is found to be successful in this trial.

In the study referenced above, the investigators found lower medication adherence and lower treatment retention with the standard (as opposed to enhanced) medical management treatment, but little difference in the amount of reduction of illicit opioid use between the EMM and the SMM conditions (Fiellin et al., 2002). However, the difference in the amount of treatment received by the two groups in this study was rather small: 15 minutes a week for the SMM group and 45 minutes a week for the EMM group ([name], personal communication). A greater contrast was chosen for our proposed study.

- For SMM Phase 1:
 - One-hour initial visit and 15-20 minute follow-up visit in Week 1.
 - Weekly 15-20 minute visit for Weeks 2-4.
 - One 15-20 minute visit in each of Weeks 6 and 8 of follow-up period.
- For SMM Phase 2:
 - One 30-60 minute initial visit and 15-20 follow-up visit in Week 1.
 - Weekly 15-20-minute visits in Weeks 2-16.

The *enhancement* will consist of individual drug counseling visits lasting approximately 45 minutes each, as follows:

- For EMM Phase 1:
 - Twice weekly individual drug counseling for Weeks 1-4.
 - One weekly individual drug counseling session in each of Weeks 6 and 8 of follow-up period.
- For EMM Phase 2:
 - Twice-weekly individual drug counseling for Weeks 1-6.
 - Once-weekly individual drug counseling in Weeks 7-12.

The enhancement in our study is additive (i.e., *in addition to SMM*) rather than comparative.

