11.2.7 Modeling of Site Effects

The outcomes of subjects from the same site are expected to be correlated. To account for these correlations in the analysis, all tests will be based on Generalized Estimating Equations (GEE) models [Diggle, PJ, Liang K-Y, and Zeger, SL (1994) Analysis of Longitudinal Data, Oxford University Press, Oxford]. GEE approach allows modeling of correlated data that is not necessarily normal, such as the primary outcomes for both Phase 1 and Phase 2. This method is generally robust with respect to misspecification of the correlation structure of the outcome in the sense that it produces unbiased estimates of the parameters in the model for the mean.

The goal of this study is to estimate an overall effect of EMM vs. SMM, rather than to study efficacy in individual sites. There is no evidence that the relative efficacy will differ between sites or that overall efficacy of EMM and SMM will be different in different sites, either for Phase 1 or for Phase 2 study. Therefore, main effects for sites and interaction between sites and treatment will be investigated only as an exploratory analysis.

The GEE approach also allows specification of more than one clustering factor. In this study, in addition to site, repeated measurements over time would constitute another clustering factor. GEE will be used to account for the correlation due to repeated measurements over time and the correlation due to correlation within site.

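### The longitudinal GEE analyses are declared valid under missing at random and robust to a wrong correlation structure; for unweighted GEE the two do not hold together if dropout follows earlier urines

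*Protocol*

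**What the plan says.** Section 11.2.4 of the protocol states that the analysis of symptom severity and "positive/negative weekly urines will be based on generalized linear models and Generalized Estimating Equations (GEE) models", run in PROC GENMOD. It says the method "provides robust inference with respect to misspecification of the covariance" and can use data with missed weeks or dropout. It concludes: "Thus, complete information for all patients is not needed".

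The next paragraph gives the validity condition: "The inferences from incomplete or missing data are valid provided that the missing data are missing at random". Missing at random (MAR) is defined there: it "means that the missing mechanism does not depend on the value of the unobserved outcome". Dropout that depends on urines already observed therefore counts as MAR. Section 11.2.7 repeats the robustness claim: "This method is generally robust with respect to misspecification of the correlation structure of the outcome", in the sense of unbiased mean parameters.

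Section 11.4.4.2 tests Hypothesis 2.2 by GEE, as a treatment-by-week interaction on 12 weekly urines. No weighting, multiple imputation or likelihood mixed model is named for this analysis, and no working correlation is stated. Two safeguards appear in 11.2.4: sensitivity analyses for missingness that depends on the unobserved value, and a rule that where a urine is missing but hard evidence of use exists, "a positive urine status will be imputed".

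**The concern.** MAR as a sufficient condition belongs to likelihood-based or suitably weighted methods. Ordinary GEE on available data needs more. Robustness to the correlation structure is a property of complete data, or of data missing completely at random or depending only on modelled covariates. The plan claims both properties at once for a setting where relapse before dropout is plausible.

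The protocol also gives some reason to expect retention to differ by arm. Section 2.3.1 reports that in an earlier study "the investigators found lower medication adherence and lower treatment retention with the standard (as opposed to enhanced) medical management treatment". If SMM participants with positive urines leave more readily, the remaining SMM sample looks better over time and the EMM-SMM slope comparison is pulled against EMM. At stake are a named secondary hypothesis and the longitudinal analyses of symptom scores.

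**Working it through.** **Why the two statements conflict.** With independence working correlation, GEE solves Σ x_t R_t (Y_t − μ_t) = 0, where R_t = 1 if the urine at week t is observed. This is unbiased only if E(Y_t | R_t = 1, X) = μ_t. If dropout depends on past urines, and past urines correlate with Y_t, the equality fails although the data are MAR by the plan's definition. A correct participant-level correlation can largely repair this, so the choice of structure matters. Replacing R_t by R_t/π_t, with π_t = P(R_t = 1 | observed history), restores the equality under MAR if π_t is modelled correctly.

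**Inputs from the protocol.**
- Phase 2 sample size 324 (11.4.3.2); 162 per arm is assumed.
- Two-sided α = 0.05 (11.2.1); weeks 1 to 12 and the interaction model (11.4.4.2).
- Treatment dropout of 5% per month: 3 × 5% = 15% as stated in 11.4.3.2, or 1 − 0.95³ = 14.3% if compounded.

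The protocol gives no type I error or bias figure for this analysis, so there is none to reproduce.

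**Assumptions not in the protocol.** logit P(opiate-free) = b₀ + u + 0.05t, with b₀ = 0.4 or −0.3, u ~ N(0, 2²) and no treatment effect. As an alternative, the latent process is AR(1) with SD 3 and ρ = 0.9. The weekly dropout hazard depends only on the last urine. Robust standard errors are used with participant as cluster. Site correlation, isolated missed weeks and the hard-data rule are not modelled. As a check on the hazards, 0.0145 per week over 11 intervals gives 1 − 0.9855¹¹ ≈ 15% dropout.

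**Rejection rate for the interaction, no true effect, independence working correlation.**

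| Dropout SMM / EMM | Weekly hazard after positive / negative urine | Unweighted | Weighted |
|---|---|---|---|
| about 18% / 12% | same ratio in both arms | 5.9% | – |
| 24.8% / 14.9% | SMM .06/.005; EMM .03/.005 | about 11% | 5% or below |
| 17.5% / 14.9% | SMM .035/.002; EMM .0145 either way | 12–13% | 4.7% |
| 18.0% / 15.2%, AR(1) | as the row above | 7.1% | 5.1% |
| 30% / 10.5% (extreme) | SMM .08/.005; EMM .01 either way | about 37% | 5% or below |
| 37.5% / 29.9% (extreme) | SMM .085/.005; EMM .032 either way | 41.0% | 3.8% |
| 38.1% / 29.8%, AR(1) (extreme) | as the row above | 14.1% | 4.6% |

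On complete data the test rejected in 4.8% to 5.3% of trials.

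**Size of the bias.** In the third row the interaction bias is −0.0134 per week. From week 1 to week 12 that is 11 × (−0.0134) = −0.15 in log odds ratio, a factor of exp(−0.15) = 0.86 against EMM.

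**Direction.** In a rerun of the 24.8%/14.9% and 30%/10.5% cases (9.6% and 37.5% rejection), false rejections favouring EMM were 0.45% and 0%. A correct test would give 2.5%.

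**Power.** With a true interaction of about 0.037 per week and the mechanism of the third row, the estimate fell to about 0.023. Power fell from 68% on complete data to 27%. Completely random dropout of 15% left power at 59%, so most of the fall is bias rather than lost information.

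**Controls.**
- Completely random dropout: interaction bias at most 0.0013.
- The same outcome-dependent hazards in both arms: the time slope moved from 0.032 to 0.045, but the interaction by at most 0.0006.
- Participant-level exchangeable correlation: bias of 0.0006 in random-intercept data and 0.0015 to 0.0053 in AR(1) data. Rejection was 3.5% to 7.0% in 200 trials, where the simulation standard error at 5% is √(0.05 × 0.95/200) = 1.5 points.
- Exchangeable correlation with site as the cluster (12 sites of 27, site SD 0.6 assumed, 120 trials): bias of −0.012 and −0.030 in the 24.8%/14.9% and 30%/10.5% cases, close to independence (−0.013 and −0.032).

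**The case against.** The strongest reply is that the protocol does not commit to independence. Section 11.2.7 says correlation over time will be accounted for, the working structure is ordinary SAP content, and a participant-level exchangeable choice nearly removes the problem. This stands as a limit on size. It does not rescue the text, which calls the choice immaterial. Section 11.2.7 also introduces the clustering through site, and a structure placed only at site level leaves the bias in place.

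Several stronger readings are tempting, and the protocol does not support them.

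- *That 15% of urines will be missing.* The 15% is treatment dropout. Sections 7.4.1 and 7.4.2.2 separate stopping treatment from stopping research visits, and 8.1.2 keeps worsening participants in follow-up. The rate of missing urines may be lower.
- *That arm-specific, outcome-dependent loss is documented.* The earlier study in 2.3.1 showed lower treatment retention under SMM. It does not report missing urines or how loss depended on outcome, and it found little difference in reduction of illicit opioid use.
- *That the hard-data rule adds to the bias.* Drug use is recorded at medical management visits, which both arms attend (10.2.3.2). Imputing positives for known users could equally offset the mechanism described. The effect was not modelled.
- *That the sensitivity analyses all inherit the fault.* The first approach in 11.2.4 re-estimates the effect under an assumed missingness model and need not start from unweighted GEE. What inherits the fault is the MAR fit used as the reference, to which the local sensitivity index is tied.

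**Conclusion.** The point holds as an error of statement with a conditional consequence. The validity and robustness sentences cannot both be true for unweighted GEE once dropout depends on earlier urines, and nothing else in the protocol repairs them.

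Bias in the Hypothesis 2.2 interaction requires both an arm-specific dropout mechanism and a working correlation that fits poorly. Under the assumptions above with participant SD 2, type I error is about 6% when the outcome-dependence ratio is the same in both arms. It is about 11% to 12% with moderate arm differences and about 37% in an extreme case. A reader might infer that the error rate is generally lost, but the milder scenarios do not show that. Nor does the problem manufacture support for EMM: almost all false rejections go the other way, so the likely cost is lost power or false evidence against EMM.

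The primary outcomes are not touched, because participants who discontinue count as failures (11.3.3.3) or as not substantially improved (11.4.3.3). The correction is worth making but is confined to secondary and exploratory longitudinal analyses.

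**What to change.** 1. **Section 11.2.4:** state that unweighted GEE on available data requires missingness completely at random or dependent only on modelled covariates. Limit the robustness statement to that case or to complete data, and make the same limitation in 11.2.7.
2. **Section 11.4.4.2:** make inverse-probability-weighted GEE the main analysis of Hypothesis 2.2, with weights from arm, prior urines and baseline variables. Cover missed weeks as well as permanent dropout. This keeps the plan's marginal odds ratio and its handling of site. Apply the same approach to the longitudinal symptom scores, with weights from their own earlier values.
3. Name a working correlation defined at participant level.
4. Use this MAR-valid fit as the reference for the sensitivity analyses in 11.2.4.

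A likelihood mixed model may be added as support. It held 5.6% to 5.9% in the 24.8%/14.9% and 30%/10.5% scenarios, but those data were generated from a random-intercept model, which favours it, and its odds ratios are participant-specific. Site should not become a fixed effect in the main model: 11.2.6 keeps the primary analysis unadjusted and 11.2.7 makes site main effects exploratory.

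The cost is wording, modest extra programming and slightly wider standard errors from weighting. Design, sample size and data collection do not change.
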